#### 12 EVALUATION CRITERIA

Although the clinical benefit of the combination of Hu5F9-G4 (magrolimab) and dinutuximab has not yet been established, the intent of offering this treatment is to provide a possible therapeutic benefit, and thus the patient will be carefully monitored for tumor response and symptom relief in addition to safety and tolerability. Patients with measurable disease will be assessed by standard criteria as outlined below.

For Arm A and Arm B cohorts 1-3, patients should be evaluated for disease status initially after Cycle 2 and Cycle 4 then after every four cycles of combination therapy, for a maximum of 12 cycles in cohorts 1 through 3. After completion of combination therapy, for patients who have not experienced disease progression, disease evaluations will continue at month 2 ( $\pm$  1 week), month 4 ( $\pm$  2 weeks), month 6 ( $\pm$  4 weeks), month 9 ( $\pm$  4 weeks), and month 12 ( $\pm$  2 months) and then every six months ( $\pm$  2 months) until year 5. Confirmatory scans will also be obtained  $\geq$  4 weeks following initial documentation of an objective response.

Patients in Arm B cohort 4, who undergo resection of all metastatic lesions (rendered NED) *before* protocol treatment, should be evaluated for disease status after Cycle 2 and after Cycle 5. After Cycle 5 for patients who have not experienced disease progression, disease evaluation will continue at month 2 ( $\pm$  1 week), month 4 ( $\pm$  2 weeks), month 6 ( $\pm$  4 weeks), month 9 ( $\pm$  4 weeks), and month 12 ( $\pm$  2 months) and then every six months ( $\pm$  2 months) until year 5.

Patients in Arm B cohort 4, who undergo staged resection *during* protocol therapy, should be evaluated for baseline disease status after their initial resection (prior to Priming Dose and Cycle 1). The subsequent disease evaluations will be performed following the second surgical resection *and* completion of two cycles (i.e., end of Cycle 3), and after five cycles (i.e., end of Cycle 6) of combination therapy. After Cycle 6 for patients who have not experienced disease progression, disease evaluation will continue at month 2 ( $\pm$  1 week), month 4 ( $\pm$  2 weeks), month 6 ( $\pm$  4 weeks), month 9 ( $\pm$  4 weeks), and month 12 ( $\pm$  2 months) and then every six months ( $\pm$  2 months) until year 5.

All measurements should be taken and recorded in metric notation using a ruler or calipers. All baseline evaluations should be performed as closely as possible to the beginning of treatment and never more than 4 weeks (within 28 days) before the beginning of the treatment.

The same method of assessment and the same technique should be used to characterize each identified and reported lesion at baseline and during follow-up. Imaging-based evaluation is preferred to evaluation by clinical examination unless the lesion(s) being followed cannot be imaged but are assessable by clinical exam.

# 12.1 Antitumor Effect – Osteosarcoma (Measurable disease)

Response and progression will be evaluated in this study using the new international criteria proposed by the revised Response Evaluation Criteria in Solid Tumors (RECIST) guideline (version 1.1) [Eur J Ca 45:228-247, 2009]. Changes in the largest diameter (unidimensional measurement) of the tumor lesions and the shortest diameter in the case of malignant lymph nodes are used in the RECIST criteria.

# 12.1.1 Definitions

Evaluable for toxicity. All patients will be evaluable for toxicity from the time of their first treatment with Hu5F9-G4 (magrolimab) (Safety Lead-In).

Evaluable for objective response. Patients must have measurable osteosarcoma at enrollment for the expansion cohort with osteosarcoma (Cohort B3). Those patients who have only received the priming dose and have received at least one dose of Hu5F9-G4 (magrolimab) followed on day 2 by dinutuximab and who do not have their disease

re-evaluated will be considered non-evaluable.

*Note*: Patients who exhibit disease progression prior to end of Cycle 2 evaluation will be considered evaluable.

#### **12.1.2** Disease Parameters

Measurable disease. Measurable lesions are defined as those that can be accurately measured in at least one dimension (longest diameter to be recorded) as  $\geq 10$  mm ( $\geq 1$  cm) with cross sectional imaging (CT scan or MRI), or calipers by clinical exam. All tumor measurements must be recorded in millimeters (or decimal fractions of centimeters).

*Note*: Tumor lesions that are situated in a previously irradiated area might be considered measurable.

Malignant lymph nodes. To be considered pathologically enlarged and measurable, a lymph node must be  $\geq$ 15 mm ( $\geq$ 1.5 cm) in short axis when assessed by CT scan (CT scan slice thickness recommended to be no greater than 5 mm [0.5 cm]). At baseline and in follow-up, only the short axis will be measured and followed.

Non-measurable disease. All other lesions (or sites of disease), including small lesions (longest diameter <10 mm [<1 cm] or pathological lymph nodes with  $\ge 10$  to <15 mm [ $\ge 1$  to <1.5 cm] short axis), are considered non-measurable disease. Bone lesions, leptomeningeal disease, ascites, pleural/pericardial effusions, lymphangitis cutis/pulmonitis, inflammatory breast disease, and abdominal masses (not followed by CT or MRI), are considered as non-measurable.

*Note*: Cystic lesions that meet the criteria for radiographically defined simple cysts should not be considered as malignant lesions (neither measurable nor non-measurable) since they are, by definition, simple cysts.

'Cystic lesions' thought to represent cystic metastases can be considered as measurable lesions, if they meet the definition of measurability described above. However, if non-cystic lesions are present in the same patient, these are preferred for selection as target lesions.

Target lesions. All measurable lesions up to a maximum of 2 lesions per organ and 5 lesions in total, representative of all involved organs, should be identified as **target lesions** and recorded and measured at baseline. Target lesions should be selected on the basis of their size (lesions with the longest diameter), be representative of all involved organs, but in addition should be those that lend themselves to reproducible repeated measurements. It may be the case that, on occasion, the largest lesion does not lend itself to reproducible measurement in which circumstance the next largest lesion which can be measured reproducibly should be selected. A sum of the diameters (longest for non-nodal lesions, short axis for nodal lesions) for all target lesions will be calculated and reported as the baseline sum diameters. If lymph nodes are to be included in the sum, then only the short axis is added into the sum. The baseline sum diameters will be used as reference to further characterize any objective tumor regression in the measurable dimension of the disease.

Non-target lesions. All other lesions (or sites of disease) including any measurable lesions over and above the 5 target lesions should be identified as **non-target lesions** and should also be recorded at baseline. Measurements of these lesions are not required, but the presence, absence, or in rare cases unequivocal progression of each should be noted throughout follow-up.

#### **12.1.3** Methods for Evaluation of Measurable Disease

Clinical lesions: Clinical lesions will only be considered measurable when they are superficial (e.g., skin nodules and palpable lymph nodes) and  $\geq 10$  mm ( $\geq 1$  cm) diameter as assessed using calipers (e.g., skin nodules). In the

case of skin lesions, documentation by color photography, including a ruler to estimate the size of the lesion, is recommended.

Conventional CT and MRI: This guideline has defined measurability of lesions on CT scan based on the assumption that CT slice thickness is 5 mm (0.5 cm) or less. If CT scans have slice thickness greater than 5 mm (0.5 cm), the minimum size for a measurable lesion should be twice the slice thickness. MRI is also acceptable.

Use of MRI remains a complex issue. MRI has excellent contrast, spatial, and temporal resolution; however, there are many image acquisition variables involved in MRI, which greatly impact image quality, lesion conspicuity, and measurement. Furthermore, the availability of MRI is variable globally. As with CT, if an MRI is performed, the technical specifications of the scanning sequences used should be optimized for the evaluation of the type and site of disease. Furthermore, as with CT, the modality used at follow-up should be the same as was used at baseline and the lesions should be measured/assessed on the same pulse sequence. It is beyond the scope of the RECIST guidelines to prescribe specific MRI pulse sequence parameters for all scanners, body parts, and diseases. Ideally, the same type of scanner should be used and the image acquisition protocol should be followed as closely as possible to prior scans. Body scans should be performed with breath-hold scanning techniques, if possible.

PET-CT: At present, the low dose or attenuation correction CT portion of a combined PET-CT is not always of optimal diagnostic CT quality for use with RECIST measurements. However, if the site can document that the CT performed as part of a PET-CT is of identical diagnostic quality to a diagnostic CT (with IV and oral contrast), then the CT portion of the PET-CT can be used for RECIST measurements and can be used interchangeably with conventional CT in accurately measuring cancer lesions over time. Note, however, that the PET portion of the CT introduces additional data which may bias an investigator if it is not routinely or serially performed.

Ultrasound: Ultrasound is not useful in assessment of lesion size and should not be used as a method of measurement. Ultrasound examinations cannot be reproduced in their entirety for independent review at a later date and, because they are operator dependent, it cannot be guaranteed that the same technique and measurements will be taken from one assessment to the next. If new lesions are identified by ultrasound in the course of the study, confirmation by CT or MRI is advised. If there is concern about radiation exposure at CT, MRI may be used instead of CT in selected instances.

Endoscopy, Laparoscopy: The utilization of these techniques for objective tumor evaluation is not advised. However, such techniques may be useful to confirm complete pathological response when biopsies are obtained or to determine relapse in trials where recurrence following complete response (CR) or surgical resection is an endpoint.

Tumor Markers: Tumor markers alone cannot be used to assess response. If markers are initially above the upper normal limit, they must normalize for a patient to be considered in complete clinical response.

Cytology, Histology These techniques can be used to differentiate between partial responses (PR) and complete responses (CR) in rare cases (*e.g.*, residual lesions in tumor types, such as germ cell tumors, where known residual benign tumors can remain).

The cytological confirmation of the neoplastic origin of any effusion that appears or worsens during treatment when the measurable tumor has met criteria for response or stable disease is mandatory to differentiate between response or stable disease (an effusion may be a side effect of the treatment) and progressive disease.

FDG-PET While FDG-PET response assessments need additional study, it is sometimes reasonable to incorporate the use of FDG-PET scanning to complement CT or MRI scanning in assessment of progression (particularly

possible 'new' disease). New lesions on the basis of FDG-PET imaging can be identified according to the following algorithm:

- a. Negative FDG-PET at baseline, with a positive FDG-PET at follow-up is a sign of PD based on a new lesion.
- b. No FDG-PET at baseline and a positive FDG-PET at follow-up: If the positive FDG-PET at follow-up corresponds to a new site of disease confirmed by CT, this is PD. If the positive FDG-PET at follow-up is not confirmed as a new site of disease on CT, additional follow-up CT scans are needed to determine if there is truly progression occurring at that site (if so, the date of PD will be the date of the initial abnormal FDG-PET scan). If the positive FDG-PET at follow-up corresponds to a pre-existing site of disease on CT that is not progressing on the basis of the anatomic images, this is not PD.
- c. FDG-PET may be used to upgrade a response to a CR in a manner similar to a biopsy in cases where a residual radiographic abnormality is thought to represent fibrosis or scarring. The use of FDG-PET in this circumstance should be prospectively described in the protocol and supported by disease-specific medical literature for the indication. However, it must be acknowledged that both approaches may lead to false positive CR due to limitations of FDG-PET and biopsy resolution/sensitivity.

*Note*: A 'positive' FDG-PET scan lesion means one which is FDG avid with an uptake greater than twice that of the surrounding tissue on the attenuation corrected image.

## 12.1.4 Response Criteria

#### 12.1.4.1 Evaluation of Target Lesions

Complete Response (CR): Disappearance of all target lesions. Any pathological lymph nodes (whether target or non-target) must have reduction in short axis to <10 mm (<1 cm).

Partial Response (PR): At least a 30% decrease in the sum of the diameters of target lesions, taking as reference the baseline sum diameters.

Progressive Disease (PD): At least a 20% increase in the sum of the diameters of target lesions, taking as reference the smallest sum on study (this includes the baseline sum if that is the smallest on study). In addition to the relative increase of 20%, the sum must also demonstrate an absolute increase of at least 5 mm (0.5 cm). (Note: the appearance of one or more new lesions is also considered progressions).

Stable Disease (SD): Neither sufficient shrinkage to qualify for PR nor sufficient increase to qualify for PD, taking as reference the smallest sum diameters while on study.

## 12.1.4.2 Evaluation of Non-Target Lesions

Complete Response (CR): Disappearance of all non-target lesions and normalization of tumor marker level. All lymph nodes must be non-pathological in size (<10 mm [<1 cm] short axis).

Note: If tumor markers are initially above the upper normal limit, they must normalize for a patient to be considered in complete clinical response.

Non-CR/Non-PD: Persistence of one or more non-target lesion(s) and/or maintenance of tumor marker level above the normal limits.

Progressive Disease (PD): Appearance of one or more new lesions and/or *unequivocal progression* of existing non-target lesions. *Unequivocal progression* should not normally trump target lesion status. It must be

representative of overall disease status change, not a single lesion increase.

Although a clear progression of "non-target" lesions only is exceptional, the opinion of the treating physician should prevail in such circumstances, and the progression status should be confirmed at a later time by the review panel (or Principal Investigator).

## 12.1.4.3 Evaluation of Best Overall Response

The best overall response is the best response recorded from the start of the treatment until disease progression/recurrence (taking as reference for progressive disease the smallest measurements recorded since the treatment started). The patient's best response assignment will depend on the achievement of both measurement and confirmation criteria.

#### For Patients with Measurable Disease (i.e., Target Disease)

Target	Non-Target	New Lesions	Overall	Best Overall Response when
Lesions	Lesions		Response	Confirmation is Required*
CR	CR	No	CR	≥4 wks. Confirmation**
CR	Non-CR/Non-PD	No	PR	
CR	Not evaluated	No	PR	>4 wks. Confirmation**
PR	Non-CR/Non-	No	PR	≥4 wks. Commination
	PD/not evaluated			
SD	Non-CR/Non-	No	SD	Documented at least once ≥4 wks.
	PD/not evaluated			from baseline**
PD	Any	Yes or No	PD	
Any	PD***	Yes or No	PD	no prior SD, PR or CR
Any	Any	Yes	PD	

\* See RECIST 1.1 manuscript for further details on what is evidence of a new lesion.

Note: Patients with a global deterioration of health status requiring discontinuation of treatment without objective evidence of disease progression at that time should be reported as "*symptomatic deterioration*." Every effort should be made to document the objective progression even after discontinuation of treatment.

#### 12.2 Response Criteria for Patients with Neuroblastoma (measurable or evaluable disease)

This study will use the revised International Neuroblastoma Response Criteria (INRC) for disease assessment (Park et al., 2017). The updated response criteria incorporate current approaches to imaging of neuroblastoma, including functional imaging. Furthermore, a standardized approach to assessment of bone marrow involvement is included. The current INRC do not include methods of disease assessment that are less sensitive and/or specific for neuroblastoma (99Tc bone scan and catecholamine levels).

#### **12.2.1** Definitions

Evaluable for toxicity: All patients will be evaluable for toxicity from the time of their first treatment with Hu5F9-G4 (magrolimab) (Safety Lead-In).

\*\* Only for non-randomized trials with response as primary endpoint.

\*\*\* In exceptional circumstances, unequivocal progression in non-target lesions may be accepted as disease progression.

Evaluable for Response: Patients must have evaluable or measurable malignant disease at enrollment for the dose escalation cohorts, and patients enrolling in the expansion cohort with neuroblastoma must have measurable OR MIBG evaluable disease at enrollment. MIBG evaluable disease for eligibility in neuroblastoma is defined as MIBG scan obtained within 3 weeks prior to study entry with positive uptake at a minimum of one site.

Those patients who have only received the priming dose and have received at least one dose of Hu5F9-G4 (magrolimab) followed on day 2 by dinutuximab and who do not have their disease re-evaluated will be considered non-evaluable.

**Note**: Patients who exhibit disease progression prior to the disease evaluation will also be considered evaluable.

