#### 3 PATIENT ELIGIBILITY

## 3.1 Eligibility Inclusion Criteria

Important note: The eligibility criteria listed below are interpreted literally and cannot be waived. All clinical and laboratory data required for determining eligibility of a patient enrolled on this trial must be available in the patient's medical or research record which will serve as the source document for verification at the time of audit.

**3.1.1** Patients must have a history of histologically or cytologically confirmed NBL or osteosarcoma.

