#### 3.1.3 Disease Status

Patients must have measurable or evaluable disease as follows:

- 3.1.3.1 Cohort B1: Confirmed neuroblastoma: measurable NBL/ganglioneuroblastoma (defined as those lesions that can be accurately measured in at least one dimension (longest diameter to be recorded) as ≥ 10 mm with cross sectional imaging (CT scan or MRI), or ≥ 10 mm with calipers by clinical exam). Chest x-ray cannot be used to determine eligibility. Lesions must be MIBG positive, PET avid (if patient has a history MIBG negative disease) or biopsy proven NBL/ganglioneuroblastoma.
- 3.1.3.2 **Cohort B2:** Evaluable NBL (MIBG and/or bone marrow disease only)
- 3.1.3.3 Cohort B3: Measurable osteosarcoma (defined as those lesions that can be accurately measured in at least one dimension (longest diameter to be recorded) as  $\geq 10$  mm ( $\geq 1$  cm) with cross sectional imaging (CT scan, MRI, or calipers by clinical exam). Chest x-ray cannot be used to determine eligibility.
- 3.1.3.4 **Cohort B4:** Patients with relapsed resectable pulmonary osteosarcoma who are scheduled for a surgical resection.

*Note:* Subjects will not have measurable disease due to recently resected pulmonary metastases. Investigational therapy must begin within three weeks of resection. Staged resections are permissible; investigational therapy will be administered in between resections. Patients should receive one cycle of investigational therapy in between resections but can receive additional cycles to accommodate the most appropriate surgical schedule as determined by the treating physicians. Every effort will be made to have at least half of this cohort (five of ten patients) be those requiring a staged resection.

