# **Expansion Cohort B2**

Evaluable disease will be evaluated with I-MIBG in conjunction with anatomical imaging or bone marrow aspiration;

FDG-PET may be used for tumors that are not MIBG-avid as per the International Neuroblastoma Response Criteria (INRC). Overall response rate (ORR) as measured by INRC: Initially 10 eligible subjects will be treated with Hu5F9-G4 (magrolimab) and dinutuximab at RP2D (including those in the safety evaluation); if 0 responses occur, enrollment will stop to this cohort. If 1 or more subjects respond, enrollment will continue to a total of 20 subjects with evaluable neuroblastoma treated at the RP2D. If 3 or more evaluable subjects with evaluable disease have a response, this combination in this cohort will be considered of sufficient interest to warrant additional study. The following Simon's optimal two stage design will be used for this cohort:

	Cumulative Number of Responses	Decision
Stage 1: Enter 10 patients	0	Terminate this cohort: agent ineffective
	1 or more	Inconclusive result, continue cohort to enroll to stage 2
Stage 2: Enter additional 10 patients	2 or less	Terminate this cohort: agent ineffective
	3 or more	Terminate this cohort: agent effective

The response criteria for this cohort will be as defined in INRC. Responses will be determined as either complete response (CR), partial response (PR), stable disease (SD), minor response (MR), or progressive disease (PD). Response rates will be calculated for the confirmed neuroblastoma cohort whose best response is a CR or PR. Response is defined relative to baseline disease. This combination will not be considered to be of sufficient interest for further evaluation if the true response rate is 5% and of sufficient activity if the true response rate is 25%. If the combination has a true response rate of 5%, the rule described above will identify it of sufficient activity for further study with a probability of 0.07 (type1 error) and the trial will have an expected sample size of 14 with 60% probability of early termination. If the combination has a true response rate of 25%, the rule described above will identify it of sufficient activity for further study with probability 0.88 (power against the alternative hypothesis P = 0.25).

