#### **BONE MARROW RESPONSE**

<sup>2 Sum of diameters is defined as the sum of the short axis of discrete lymph nodes (i.e., cervical, axillary nodes) added to the sum of the longest diameters of non-lymph node soft tissue metastases. Masses of conglomerate non-discrete lymph nodes will be measured using longest diameter.

<sup>3 For patients with soft tissue metastatic disease, resolution of MIBG and/or FDG-PET uptake at the soft tissue sites is not required; all size reduction criteria must be fulfilled.

<sup>4Relative Curie score is the absolute score for bone lesions at time of response assessment divided by the absolute score for bone lesions at entry onto a clinical trial. MIBG-SPECT or MIBG-SPECT/CT may be used for scoring purposes, but the same imaging methodology should be used for all evaluations.

RESPONSE	BONE MARROW STATUS 		
Complete Response (CR)	Bone marrow with no tumor infiltration upon reassessment, independent of baseline tumor involvement		
Progressive Disease (PD)	
 
Any of the following:         
 
Bone marrow without tumor infiltration that becomes > 5% tumor infiltration upon reassessment; or
 
Bone marrow with tumor infiltration that increases by > 2-fold and has > 20% tumor infiltration upon reassessment.
 
 
 
		
Minimal Disease (MD)	
 
Any of the following:         
 
Bone marrow with ≤ 5% tumor infiltration and remains > 0-≤ 5% tumor infiltration upon reassessment; or
 
Bone marrow with no tumor infiltration that becomes ≤ 5% tumor infiltration upon reassessment; or
 
Bone marrow with >20% tumor infiltration that has > 0-≤ 5% tumor infiltration upon reassessment.
 
 
 
		
Stable Disease (SD)	Bone marrow with tumor infiltration that remains positive with > 5% tumor infiltration upon reassessment but does not meet CR, MD or PD criteria		

<sup>1 Immunohistochemistry strongly encouraged

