#### **DETERMINATION OF OVERALL RESPONSE**

RESPONSE	CRITERIA
Complete Response (CR)	All components meet criteria for CR
Partial Response (PR)	PR in at least one component and all other components are either CR, MD (Bone marrow), PR (Soft tissue or Bone) or Not involved (NI); no component with PD.
Minor Response (MR)	PR or CR in at least one component but at least one other component with SD; no component with PD.
Stable Disease (SD)	SD in one component with no better than SD or NI in any other component; no component with PD.
Progressive Disease (PD)	Any component with PD

NI = Not involved, site not involved at study entry and remains not involved; MD = Minimal Disease, for bone marrow assessment only.

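### Section 12.2.1 omits bone-marrow-only disease from the response-evaluable definition although cohort B2 enrolls it; if that definition feeds the B2 final rule, a valid marrow response goes uncounted

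*Combined protocol and SAP*

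**What the plan says.** **Who enters B2.** Section 3.1.3.2 defines the cohort as "Evaluable NBL (MIBG and/or bone marrow disease only". Section 3.1 adds: "The eligibility criteria listed below are interpreted literally and cannot be waived". A patient whose only disease is in the marrow is therefore eligible.

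**How B2 is assessed.** Section 9.2.2 (Expansion Cohort B2) uses MIBG "in conjunction with anatomical imaging or bone marrow aspiration", and allows FDG-PET for tumors that are not MIBG-avid. Section 12.2.3 defines marrow complete response as "Bone marrow with no tumor infiltration upon reassessment, independent of baseline tumor involvement". Overall complete response applies when "All components meet criteria for CR".

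**How B2 is decided.** Stage 1 treats 10 eligible subjects and stops at 0 responses. The final rule, at 20 subjects, begins: "If 3 or more evaluable subjects with evaluable disease have a response". The same text adds: "Response rates will be calculated for the confirmed neuroblastoma cohort whose best response is a CR or PR". That names the cohort by the label that belongs to B1.

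**Who is evaluable for response.** Section 12.2.1 says that "patients enrolling in the expansion cohort with neuroblastoma must have measurable OR MIBG evaluable disease at enrollment", and defines MIBG-evaluable as uptake at one site or more. Section 9.5.2 instead makes every eligible patient given any dose of the combination evaluable. Sections 12.1.1 and 12.2.1 also call certain patients without re-evaluation non-evaluable, but keep those who progress before the assessment.

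**The concern.** A marrow-only patient meets 3.1.3.2 but neither limb of the 12.2.1 requirement. The same holds for a B2 patient followed by FDG-PET because the tumor is not MIBG-avid, if nothing is measurable.

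Section 9.2.2 uses the word evaluable in its final rule without defining it. An analyst looking for a definition finds two. Section 9.5.2 counts the patient; 12.2.1, under a heading about response evaluability, does not. Reading 12.2.1 as an eligibility statement does not help, because it then contradicts 3.1.3.2.

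The B2 decision turns on single patients: 2 against 3 responses among 20 separates ineffective from effective. If the third response is a marrow complete response in a marrow-only patient, the conclusion depends on which section is consulted. That should be settled before responses are counted.

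**Working it through.** **1. Reproduce the design.** Inputs from 9.2.2: n1 = 10, stop at 0; n = 20, success at 3 or more; rates 5% and 25%. With X responses in stage 1 and Y in stage 2, both binomial(10, p):

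P(success) = P(X=1)·P(Y≥2) + P(X=2)·P(Y≥1) + P(X≥3)

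- p = 0.25: 0.1877 × 0.7560 + 0.2816 × 0.9437 + 0.4744 = 0.882
- p = 0.05: 0.3151 × 0.0861 + 0.0746 × 0.4013 + 0.0115 = 0.069
- Early termination at 5%: 0.95^10 = 0.599; expected size 10 + 10 × (1 − 0.599) = 14.0

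These match the stated 0.88, 0.07, 60% and 14.

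**2. What a marrow-only patient can contribute.** The marrow table in 12.2.3 has no partial response category, and overall partial response needs a partial response in some component. A marrow-only patient can therefore count only through complete response.

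**3. Effect of not counting those responses (illustration).** Assume a share f of B2 is marrow-only and every patient responds at 25%. The countable rate is c = 0.25(1 − f).

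- *Applied at both stages:* put p = c in the formula above.
- *Applied at the final count only:* stage 1 still passes on any response, so add [(1 − c)^10 − 0.75^10] × P(Y≥3 at rate c). At f = 0.2: (0.1074 − 0.0563) × 0.3222 = 0.0165, and 0.7593 + 0.0165 = 0.776.

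| Marrow-only share f | 10% | 20% | 30% |
|---|---|---|---|
| Power, all responses counted | 0.882 | 0.882 | 0.882 |
| Power, 12.2.1 at final count only | 0.838 | 0.776 | 0.692 |
| Power, 12.2.1 at both stages | 0.829 | 0.759 | 0.670 |
| Chance of stopping at 10, both stages | 0.078 | 0.107 | 0.146 |
| Type I error, both stages (p = 0.05(1 − f)) | 0.053 | 0.040 | 0.028 |

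If only the final count is affected, the chance of stopping at 10 stays at 0.75^10 = 0.056.

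**4. Sensitivity to the marrow complete response rate q.** Others stay at 25%. If counted, p = 0.25(1 − f) + qf. Loss is the power when counted minus the power when not counted at either stage, for f = 10 / 20 / 30%:

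- q = 25%: 0.053 / 0.123 / 0.213
- q = 10%: 0.023 / 0.058 / 0.105
- q = 5%: 0.012 / 0.030 / 0.056

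**5. Patients never re-assessed.** The exclusion sentence in 12.1.1 and 12.2.1 requires a patient to have had only the priming dose and also a magrolimab dose followed by dinutuximab. No one can satisfy both. On its evident intent it drops dosed patients with neither re-evaluation nor progression, whom 9.5.2 keeps. With 3 responses the reported rate is 3/20 = 15.0%, 3/18 = 16.7% or 3/16 = 18.8% for 0, 2 or 4 such patients. The number of responses is 3 in each case.

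**The case against.** The strongest reply is that the statistics section already answers the question. Under 9.5.2 an eligible patient given any combination dose is evaluable, and a marrow-only patient is eligible. In the final rule, evaluable disease most naturally echoes B2's own name, which includes marrow disease. Parts of 12.2.1 read like an enrollment statement that was not kept in step with 3.1.3.2, and its only express non-evaluable sentence concerns missing re-evaluation. All of this stands, and makes counting the marrow-only patient the better reading. It does not remove the conflict: 9.5.2 sits under a secondary objective, no passage gives one section precedence, and 12.2.1 is the section headed with the definition.

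A reader might infer that 12.2.1 also threatens the stage 1 decision. The documents do not support that as written: stage 1 counts responses among eligible treated subjects, with no evaluability condition. It is affected only if 12.2.1 is imported there.

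A reader might also take the power figures as an established loss. They are not; share and response rate are both assumed, and the loss ranges from 0.012 to 0.213 over the both-stage cases shown.

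Finally, one might infer that unassessed patients alter the go/no-go result. They do not. An unassessed patient has no recorded response under either rule, 9.3.3 plans 20 per cohort, and no passage provides for replacing a patient for response. Read literally, the exclusion sentence removes nobody, so that conflict rests on its evident intent.

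**Conclusion.** The contradiction between 12.2.1 and 3.1.3.2, 9.2.2 and 9.5.2 is plain on the text and needs no assumption. It matters if 12.2.1 supplies the meaning of evaluable in the B2 final rule: one marrow complete response can then change the conclusion. With marrow-only shares of 10 to 30% and a 25% rate throughout, power would be 0.838 to 0.692 rather than 0.882; lower marrow response rates make the loss smaller. Because type I error also falls, the exposure is to overlooking activity, not to claiming it falsely. The design arithmetic is correct.

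The wording on unassessed patients is a minor point. It changes the reported response rate and leaves the two-stage decision alone.

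**What to change.** 1. In 12.2.1, make the response-evaluable definition for B2 match 3.1.3.2 and 9.2.2: MIBG-positive disease, FDG-PET-avid disease where the tumor is not MIBG-avid, and/or bone marrow disease. Adding marrow alone would still leave out the FDG-PET patients.
2. In the B2 text of 9.2.2, replace the B1 label with the B2 cohort name.
3. Rewrite the exclusion sentence in 12.1.1 and 12.2.1 to agree with 9.5.2: the denominator for B1 to B3 is all eligible patients given any combination dose, and those with no post-baseline assessment count as non-responders. Another denominator could be defended, but this one is already in the statistics section, and one rule must apply throughout.

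The cost is a wording amendment to three sections. It needs no extra patients, scans or samples, since marrow evaluation is already required at every neuroblastoma disease assessment. The drawback is a slightly lower reported response rate when patients go unassessed, for example 15.0% rather than 18.8% with 3 responses and 4 of 20 unassessed.
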